		4.6.3 Concomitant Medications or Antiretroviral Therapies	14
		4.6.4 Study Treatment Initiation Method	15
		4.6.5 Study Treatments	15
	4.7	Analysis of Clinical Study Endpoints	15
		4.7.1 Safety Analysis	15
		4.7.2 Clinical Laboratory Assessments	18
		4.7.3 Changes in Vital Signs	19
		4.7.4 Effectiveness	19

	4.7.5 Use of Oral Bridging	20
	4.7.6 Impact of COVID-19 Pandemic	20
	4.7.7 Changes from Planned Analysis	20
5	LIMITATIONS ON RESEARCH METHODS	20
6	REFERENCES	21
7	APPENDICES	22
	7.1 Schedule of Activities (SoA)	22
	7.2 Protocol Deviations Rules Document	25
	7.3 Tables and Listings	25
	7.3.1 Tables	25
	7.3.2 Listings	27

List of Tables

Table 1.	Clinical Objectives and Endpoints	4
List of	f Figures	
Figure 1.	Study Design Schematic	2

List of Abbreviations

Abbreviation	Definition
ADR	Adverse drug reaction
AE	Adverse event
ALP	Alkaline phosphatase
ALT	Alanine aminotransferase
ART	Antiretroviral therapy
ASA	Alternative site of administration
AST	Aspartate aminotransferase
BMI	Body mass index
CAB	CABENUVA
CI	Confidence interval
DBL	Database lock
ECG	Electrocardiogram
eCRF	Electronic case report form
HIV	Human immunodeficiency virus
IC	Infusion center
ICF	Informed consent form
IM	Intramuscular
IQR	Interquartile range
MedDRA	Medical Dictionary for Regulatory Activities
PLWHIV	People living with human immunodeficiency virus
POT	Plan of treatment
PT	Preferred term
Q1M	Once monthly
Q2M	Once every -2 -months
RNA	Ribonucleic acid
RPV	EDURANT
SAE	Serious adverse event
SAP	Statistical analysis plan
SD	Standard deviation
SGOT	Serum glutamic-oxaloacetic transaminase
SGPT	Serum glutamic-pyruvic transaminase
SoA	Schedule of activities
SOC	System organ class
SRM	Study reference manual
ULN	Upper limit of normal
USPI	United States prescribing information

1 Introduction

CABENUVA is a two-drug, co-packaged product of cabotegravir plus rilpivirine, both administered as long-acting, intramuscular (IM) injections once every month or once every 2 months. CABENUVA is an approved treatment for human immunodeficiency virus (HIV). Clinical trial results have shown that CABENUVA, administered once monthly or once every 2-months, is a non-inferior alternative to the daily oral treatment for HIV.

Long-acting injectable treatments require changes in how HIV care is delivered. People living with human immunodeficiency virus (PLWHIV) need to attend appointments once a month or once every 2 months for their injections, increasing office visits over their normal monitoring visits. This poses new healthcare delivery challenges, including a shift in resources to this alternative means of delivering and receiving treatment—thus requiring the expansion of alternative injection facilities to include infusion centers (ICs) or other alternative sites of administration (ASAs). This has the potential to increase the workload for these facilities; however, it also has the potential to positively impact treatment engagement and retention for PLWHIV.

ICs/ASAs are an appealing option that will help ease the burden of additional appointments, administrative work, and drug ordering in HIV specialty clinics, as well as provide greater flexibility to PLWHIV in deciding where they receive their monthly or every-2-monthly injections. In this study, the intervention itself is the process of using an IC/ASA as the location to receive the CABENUVA IM injections.

The scope of this statistical analysis plan (SAP) is to examine the safety and effectiveness of CABENUVA IM injections in real-world settings through ICs/ASAs. This SAP details the planned analyses for the tertiary objectives that are related to the safety and effectiveness of CABENUVA, as outlined in Table 1 in Section 3. It implements the study's clinical objectives and endpoints and specifies the needed summary tables and other statistical results of the lab tests, other clinical metrics, CABENUVA-related adverse events (AEs), all AEs leading to participant discontinuation, all cardiovascular events, COVID-19 related, and all serious AEs (SAEs). Two analysis sets will be used for the study analyses: the Enrolled Set and the Safety Set. The Enrolled Set will include all participants who provided a signed informed consent form (ICF), met the eligibility criteria, and were enrolled in the study. The Safety Set will consist of all participants in the Enrolled Set who received at least one on-study CABENUVA injection(s).

2 Study Design

This is a phase 4, single-arm, open-label, multicenter study examining the administration of CABENUVA IM in ICs/ASAs across the US. This study is being conducted following FDA approval and commercial availability of CABENUVA in the US.

[figure not shown]
This study will include no more than 120 eligible and consenting participants to receive monthly injections or every-2-monthly injections of CABENUVA for HIV-1 treatment at ICs/ASAs. The total study duration for each participant is approximately 8 months, from the time of their enrollment and receipt of the first

study-related administration of CABENUVA IM injections at the IC/ASA. For a detailed Schedule of Activities (SoA), refer to Appendix 7.1. CABENUVA dosing adherence is described in the US prescribing information (USPI) if CABENUVA injections were missed.

Figure 1. Study Design Schematic

Participant assessments are completed based on Month regardless of monthly (Q1M) vs. every-2-monthly (Q2M) dosing. Note: Study design may not include all potential patterns of dosing.

2.1 Study Population

The study aims to recruit no more than 120 participants who have been prescribed CABENUVA by their HIV care provider. During their first visit to the IC/ASA, after signing an ICF, participants will complete baseline assessments to confirm participant eligibility and then receive their Month 1 injections. In subsequent months, participants are medically managed by their HIV care providers and receive their once-a-month or every-2-months injections at the IC/ASA.

Over time, participant treatment discontinuation as well as missed injections are expected. PLWHIV are allowed in the study if they have been prescribed CABENUVA per the USPI and meet all eligibility criteria (Section 2.1.1) at the Baseline/Month 1 visit. Participants who sign the ICF and meet all eligibility criteria will enter the study.

If a participant plans to miss the injections by more than 7 days, in consultation with the HIV care provider, oral CABENUVA plus EDURANT (CAB + RPV) or other antiretroviral therapy (ART) regimens should be taken daily to replace up to two consecutive planned missed monthly injection visits or every-2-month injection visit-doses. Dosing of oral bridging in the event of missed doses will be in accordance with the most recent CABENUVA USPI.

In consultation with the HIV care provider, participants may switch from monthly injections to an every-2-month continuation injection schedule, or from a 2-month continuation injection schedule to a monthly continuation dosing schedule. When switching dosing regimens, all instructions outlined in the most current USPI will be followed. The total duration for study participants is approximately 8 months from

the time of enrollment and receipt of the first study-related administration of CABENUVA IM injections at the IC/ASA. A participant is considered to have completed the study if they have finished all Month 8 assessments.

2.1.1 Eligibility Criteria

The eligibility criteria below are the most current as of the writing of the SAP.

2.1.1.1 Inclusion Criteria

Age

1. Adults (≥18 years old) at the time of signing the ICF

Type of Participant and Disease Characteristics

- 2. PLWHIV-1, prescribed CABNEUVA per the USPI. Participants can be enrolled:
- If they have been taking oral CAB + RPV or other ART for approximately 1 month (at least 28 days) prior to Baseline/Month 1, or
- Already taking CABENUVA prior to Baseline/Month 1 and the last injections were within a 1-month \pm 7-day window, or for every-2-month injections, the timing will vary depending on when they are receiving the initiation injections (1 month \pm 7 days) or the continuation injections (2 months \pm 7 days) per the USPI, or
- Prescribed direct to inject and receive their first injection without an oral lead-in at the IC/ASA on the last day of any other ART

Informed Consent

3. Capable of giving signed informed consent as described in the protocol, which includes compliance with the requirements and restrictions listed in the ICF and in the protocol.

Other

4. Agree to receive CABENUVA IM injections at participating ICs/ASAs.

2.1.1.2 Exclusion Criteria

Participants may be excluded from the study, in consultation with the HIV care provider, based on information from the most current CABENUVA USPI at the time of study enrollment.

Contraindications, as per the current CABENUVA USPI

- Previous hypersensitivity reaction to cabotegravir or rilpivirine
- Contraindicated co-administered drugs:
 - o Anticonvulsants: carbamazepine, oxcarbazepine, phenobarbital, phenytoin
 - o Antimycobacterials: rifabutin, rifampin, rifapentine
 - Glucocorticoid (systemic): dexamethasone (more than a single-dose treatment)
 - Herbal product: St John's wort (Hypericum perforatum)

New health condition / prohibited medication reported

[figure not shown]
 After discussion with the referring HIV care provider, a decision may be made not to enter participant into the study

Other reason at the discretion of the HIV care provider or IC/ASA staff

3 Objectives and Endpoints

The scope of this SAP is limited to the clinical objectives and endpoints related to the safety and effectiveness of CABENUVA as set forth in the protocol (see Table 1).

Table 1. Clinical Objectives and Endpoints

3.1 Primary Objectives

[figure not shown]
The primary objectives are beyond the scope of this clinical SAP. Three additional implementation research SAPs are planned and will cover the primary objectives, one each for participant type (participants living with HIV, healthcare providers and expert panel members, and infusion center staff).

[figure not shown]
3.2 Secondary Objectives

The secondary objectives are beyond the scope of this clinical SAP. Three additional implementation research SAPs are planned and will cover the secondary objectives, one each for participant type (participants living with HIV, healthcare providers and expert panel members, and infusion center staff).

3.3 Tertiary Objectives

4 Statistical Methods

4.1 General Statistical Considerations

Data will be analyzed on the nominal scheduled visits as recorded in the eCRF. Visit windowing will be used as required.

4.1.1 Descriptive Summary Statistics

If the number of non-missing observations is zero (i.e., n=0), then only n is displayed, no other statistics. Two-sided 95% confidence intervals (CIs) will be provided using normal approximation. But when normal approximation is deemed to be inappropriate, exact methods will be used instead.

4.1.1.1 Categorical Data

Tabulations for categorical data will be displayed in the form n (%) with non-zero percentages enclosed with parentheses.

The number of distinct participants with non-missing observations (n) at all levels of categories will be presented. If no participants are reported for a particular level of a category, n will be presented as zero. If for all levels of a category, data are missing for at least one participant, a "Missing" category level will be presented.

Percentages (%) will be presented when there is at least one non-missing observation. Percentages will not be presented for the "Missing" category level. Percentages >99.9% will be displayed as 100%; in other cases, they will be rounded to and displayed with one decimal place. Generally, the denominator for percentages will be the number of participants in the analysis group of interest for the specified analysis set. Other denominators will be described in a footnote when applicable.

4.1.1.2 Continuous Data

The following summary statistics will be reported for continuous data:

- n: number of distinct participants with non-missing observations
- Mean (standard deviation [SD]): arithmetic mean, SD)
- Median
- Interquartile range (IQR; i.e., 25th percentile [Q1] 75th percentile [Q3])
- Min, Max: minimum, maximum

If n=1, SD will be displayed as "N/A" (i.e., not applicable) and CIs as "NE" (i.e., not estimable). SD will be rounded and displayed with two more decimal places than the reported value. All mean, median, Q1, and Q3 values will be rounded and displayed to one more decimal place than the reported value. CI values will be rounded and displayed to one more decimal place than the parameter estimate. Min and max values will be displayed consistent with the number of decimal places in the reported value.

4.1.2 Baseline Definition

Baseline will be defined as the date when a participant signs the ICF and completes the Baseline/Month 1 protocol procedures prior to receiving the first study-related CABENUVA injections at the IC/ASA.

All additional study visits will be anchored from each participant's Baseline/Month 1 visit, and will therefore reflect the months on study, regardless of what injection schedule they are on and regardless of whether they have missed any injections and received oral bridging.

Change from baseline will be calculated as the difference between the baseline and post-baseline values, which have the same number of decimal places. Percent change from baseline will be calculated by dividing change from baseline by non-zero baseline value, rounded and reported to one decimal place.

4.1.3 Missing Data Handling

For the purposes of classifying medications/therapies as prior or concomitant, or for AEs as pretreatment, on-treatment, or post-treatment, incomplete dates may be imputed.

Details for handing missing AE relatedness, severity, seriousness, etc. are discussed in Section 4.7.1.1.

No other missing data will be imputed.

4.1.3.1 Imputation of Incomplete Dates

4.1.3.1.1 General Dates, including Start/Stop Dates of Concomitant Medications/Therapies

A partial event start date, or partial start dates of prior and concomitant medications/therapies, will be assumed to be the earliest possible date consistent with the partial date.

- If the day is missing, it will be assumed to be the first day of the month
- If the month is missing, it will be assumed to be January
- If the entire date is missing, assume exposure prior to dosing start and date will not be imputed

If the month and the year of the start date is the same month and year of the CABENUVA treatment start date, then the following imputation rules apply:

- If the stop date contains a full date and is earlier than the CABENUVA treatment start date, then the set start date = 1st of month
- Else, the set start date = the CABENUVA treatment start date

If the year of the start date is the same year of the CABENUVA treatment start date, then the following imputation rules apply:

- If the stop date contains a full date and is earlier than the CABENUVA treatment start date, then the set start date = January 1
- Else, the set start date = the CABENUVA treatment start date

Partial event or medication/therapy stop dates will be assumed to be the latest possible date consistent with the partial date.

- If the day is missing, it will be assumed to be the last day of the month
- If the month is missing, it will be assumed to be December
- If the entire date is missing, there will be no imputation

Note that if the concomitant medications/therapies end date is present, the imputed onset date will always be on or prior to the end date.

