4.1.3.1.2 Onset and End Dates of Adverse Event

Incomplete AE onset and end dates will be imputed, respectively, as the earliest and latest possible date consistent with the partial date and assigned treatment period (pre-study, pre-treatment or ontreatment), where:

- Pre-study: The onset of the AE is on or after the CABENUVA treatment start date, but prior to enrollment in the study
- Post-enrollment, pre-treatment: The onset of the AE is prior to the on-study CABENUVA treatment start date

 Post-enrollment, on-treatment: The onset of the AE is on or after the on-study CABENUVA treatment start date

If the event start day is missing, assume the first day of the month. If the month or entire start date are missing, assume the event occurred on January 1 if the year of the start date is not the year of the CABENUVA treatment start. If the year of the start date is the year of CABENUVA treatment start, then the following imputation rules apply:

- If the stop date contains a full date and is earlier than the CABENUVA treatment start date, then the set start date = January 1
- Else, the set start date = the CABENUVA treatment start date

If the event end day is missing, assume the last day of the month. If the month or entire end date are missing, there will be no imputation.

Events that that begin on or after the date of on-study CABENUVA treatment initiation will be considered treatment-emergent events.

Note that if the AE end date is present, the imputed onset date will always be on or prior to the end date.

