4.7.5 Use of Oral Bridging

When a participant plans for a missed injection, the participants may elect for oral bridging. Dosing of oral bridging in the event of missed doses will be in accordance with the most recent CABENUVA USPI.

A single occurrence of oral bridging will be defined as the period between two adjacent CABENUVA injections. If the participant is on oral bridging at the end of the study period, then the last occurrence of oral bridging is counted as between the last CABENUVA injection and the end of the study period. The duration of each oral bridging instance will be derived as the duration from start to end date of the use of oral HIV medication between two adjacent CABENUVA injections.

The number of occurrences and duration of each occurrence of oral bridging will be summarized in a table using the Safety Set.

Participants who have used oral bridging at least once will be summarized. This includes both the participants on a monthly injection schedule and an every-2-month injection schedule.

Frequency of the oral bridging occurrences will be summarized in a table and a histogram. This includes both the participants on a monthly injection schedule and an every-2-month injection schedule, while the max frequency for the former is eight and for the latter is four.

The missed injection rate at each visit for participants on oral bridging (proportion of participants who missed injection at scheduled visit N+1 while on oral bridging after visit N) will be summarized. Missed injection rate will be defined as one minus the adherence rate.

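### Clinical SAP 4.1.3.1.1: the same-year start-date rule does not require a missing month, so as written it overrides a known month and can remove prior status from earlier ART and medications

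*SAP*

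**What the plan says.** Clinical SAP 4.1.3.1.1 handles partial start dates of prior and concomitant medications and therapies in three layers.

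- **Lead rule.** The start "will be assumed to be the earliest possible date consistent with the partial date". For a known month this means: "If the day is missing, it will be assumed to be the first day of the month". A missing month becomes January. A wholly missing date is not imputed, and exposure is taken to precede dosing.
- **Same-month block.** It opens "If the month and the year of the start date is the same month and year of the CABENUVA treatment start date". A full stop date before CABENUVA start gives the 1st of the month; otherwise the start becomes the CABENUVA start date.
- **Same-year block.** It opens "If the year of the start date is the same year of the CABENUVA treatment start date, then the following imputation rules apply". A full stop date before CABENUVA start leads to "then the set start date = January 1". All remaining records follow "Else, the set start date = the CABENUVA treatment start date".

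The parallel adverse-event rule in 4.1.3.1.2 reaches its same-year step only after the sentence "If the month or entire start date are missing, assume the event occurred on January 1".

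Section 4.1.3 limits date imputation to classifying medications as prior or concomitant and placing AEs in a study period. Section 4.6 counts a therapy as prior if it was taken or started before the first dose of study drug.

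**The concern.** The same-year block tests only the year. A record with a known month in that year therefore meets both the lead rule and the same-year block, and the two give different dates. No order of precedence is stated, so two programmers could follow the text faithfully and produce different datasets.

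What is at stake is the prior/concomitant classification, the stated purpose of the imputation for medications. A start moved onto the first-dose date no longer precedes the first dose. The records exposed are ordinary ones. New starters come from oral lead-in or other ART. The schedule of activities (Protocol Annex 1, SAP 7.1) puts the final oral dose on the day of the first injection, and direct-to-injection participants receive the first injection on the last day of their previous ART. A stop on that day is not earlier than CABENUVA start, so the exception does not apply and the start is moved.

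**Working it through.** The plan gives no figure for this rule, so there is none to reproduce. The check applies each layer literally to the same records. The dates are illustrative, with CABENUVA started on study on 15 Aug 2022.

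| Recorded start | Recorded stop | Lead or same-month rule | Same-year block | Prior by date? |
|---|---|---|---|---|
| Mar 2022, day unknown | 15 Aug 2022 | 1 Mar 2022 | 15 Aug 2022 | yes, then no |
| Jul 2022, day unknown (28-day lead-in) | 15 Aug 2022 | 1 Jul 2022 | 15 Aug 2022 | yes, then no |
| Mar 2022, day unknown | 30 Jun 2022 | 1 Mar 2022 | 1 Jan 2022 | yes under both |
| Aug 2022, day unknown | 10 Aug 2022 | 1 Aug 2022 (same-month block) | 1 Jan 2022 | yes under both |
| Oct 2022, day unknown | 5 Nov 2022 | 1 Oct 2022 | 15 Aug 2022 | no under both |

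**Row 1.** From 1 Mar to 15 Aug is 31 + 30 + 31 + 30 + 31 + 14 = 167 days. The imputed date lies outside the recorded month.

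**Row 2.** Suppose a 28-day lead-in truly starts on day *s* of a month and the injection falls in the next month. The distance from the 1st of the known month to the injection is 28 + (*s* − 1) days. In the example the true start is 18 Jul, so 28 + 17 = 45 days.
- Smallest value: *s* = 1, possible only in a 28-day February, gives 28.
- Largest value: *s* = 31 gives 28 + 30 = 58.
- Averaged over injection days in a 365-day year, the mean is about 44 days.

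**Older starts.** With every injection day in a 365-day year and every earlier known month, the shift runs from 28 to 364 days (a January start with a 31 December injection gives 364). If months and injection days are assumed to be spread evenly, the mean is about 147 days. That even spread is an assumption; the documents do not say how start dates are distributed. In all of these cases the imputed start equals the first-dose date, so the date-based prior flag is lost.

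**Rows 3 and 4.** With a full earlier stop date the start goes to January 1. That conflicts with the recorded month, and in row 4 with the same-month block, but the therapy stays prior.

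**Row 5.** Therapy started in a later month is concomitant under either date.

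One comparison shows the inconsistency plainly. A therapy with no start date at all is treated as preceding dosing, whereas the row 1 therapy, whose earlier month is known, is treated as starting on the dosing day.

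**The case against.** The strongest reply is that the intended meaning can be inferred. The lead rule governs the section, and a separate same-month block makes sense only if the same-year block is for dates with no month. The AE rule does not repeat the missing-month condition in its own same-year sentence either; it inherits it from the sentence before. This stands as evidence of intent. It does not settle the text, because 4.1.3.1.1 has no such lead-in sentence and states no precedence.

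A second reply also stands in part. Section 4.1.3.1.2 distinguishes the CABENUVA start from the on-study CABENUVA start, and participants may enter already on CABENUVA. If 4.1.3.1.1 means the original, pre-study start, a therapy moved to that date still precedes the first on-study dose and stays prior. The loss is then confined to participants for whom the two dates coincide.

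Three stronger readings are tempting, and the documents do not support them:

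- **That every partial date in the start year goes to the CABENUVA start date.** Records with a full earlier stop date go to January 1.
- **That known months typically move by about four months.** Such a figure is only an average under an assumed even spread of dates; a 28-day lead-in moves 28 to 58 days.
- **That oral-bridging durations are distorted.** Section 4.7.5 has the duration "derived as the duration from start to end date of the use of oral HIV medication between two adjacent CABENUVA injections", but 4.1.3 allows date imputation only for classification, and bridging therapy is concomitant on either date.

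**Conclusion.** The point holds as a drafting defect whose literal reading gives a wrong date. The affected records have a known start month before the CABENUVA start month in the same year, a missing day, and either ongoing use or a stop on the first injection day. Each loses its date-based prior status if the block is programmed as written and the CABENUVA start date is the first study dose. The effect falls on the descriptive summaries of prior medications and prior ART (Tables 14.1.5 and 14.1.6).

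The documents do not show how many records have this pattern, so no percentage of misclassified participants can be given. The primary FIM endpoint does not use these dates. The point deserves correction because it is cheap and removes a contradiction, not because it threatens the study's main conclusions.

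**What to change.** In clinical SAP 4.1.3.1.1:

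1. Open the same-year block with the missing condition, for example: *If the month is missing and the start year equals the year of CABENUVA treatment start*.
2. State that a known month is never overridden, so a missing day in a month other than the CABENUVA start month becomes the 1st of that month. In the examples with a known month other than August, the shift then falls to zero and the prior flag follows the recorded month. The same-month block keeps its own rule without overlap.
3. Say whether the CABENUVA treatment start date in this section means the on-study start, using the same terms as 4.1.3.1.2 and 4.6.

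The cost is one clause and two sentences in the SAP, plus a check that the date-imputation program matches. No data collection changes.
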